2.2.3 Dose Regimen

The following three formulations have identical appearance: 1% DS107 cream, 5% DS107 cream and Vehicle cream in a 1:1:1 ratio, respectively. The medication assigned by randomization will be topically applied liberally by the patients to all affected or commonly affected areas twice daily (morning and evening) for 8 weeks. Tabulations of exposure to study medication are described in Section 2.2.13.1, Extent of Exposure. Details of study medication use will be provided in a subject data listing.

2.2.4 Study Populations for Analysis

2.2.4.1 Full Analysis Set (FAS)

The FAS consists of all patients who are randomized to the study and received at least one dose of study medication. FAS is the primary analysis population for efficacy endpoints. Analysis will be done according to the treatment patients were randomized to.

2.2.4.2 Safety Analysis Set (SS)

The SS consists of all patients who received at least one dose of the medication. SS is the analysis population for all safety endpoints. Analysis will be done according to the actual treatment patients received.

2.2.4.3 Per-Protocol Analysis Set (PPS)

The PPS is the subset of FAS who completed the study without any major violations. Protocol violations will be assessed for each patient in a blinded fashion prior to database lock at a Blind Data Review Meeting (BDRM), and the PPS will also be finalized during this meeting. PPS is a supportive analysis population for the primary efficacy endpoint. Analysis will be done according to the treatment that patients were randomized to.

2.2.4.4 Subgroup Analyses

Subgroup analyses will be conducted on the primary and secondary endpoints stratifying by severity of atopic dermatitis (mild or moderate), defined as an IGA score of 2=mild or 3=moderate at the Baseline/visit 2 visit, which is consistent with the AD severity used for the entrance criteria in the study. Statistical testing for this subgroup analyses will be limited to the primary efficacy endpoint but summary statistics will be provided for all secondary efficacy endpoints.

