2.2.8 Statistical Hypotheses

The original null hypothesis (H_0) for each analysis is the equality of the means for the three treatment groups. A global test was to be performed across all three treatment groups. The test will still be performed

The revised primary focus will be the separate comparisons of the two DS107 concentrations vs. vehicle control using a Dunnett’s correction (two-sided 97.4% confidence intervals and two-sided $p=0.026$) to reach statistical significance. The null hypotheses are the pairwise comparisons of the equality of the two DS107 concentrations vs. vehicle. Dunnett’s procedure will be used to adjust for the multiple comparisons. The overall 5% Type I error rate is controlled for by the Dunnett’s correction for multiple comparisons.

Testing between the two active groups will be considered as descriptive statistics.

All statistical testing will be two-sided; global tests will be performed at the 0.05 level while all pairwise DS107 comparisons vs vehicle will be performed at the 0.026 level.

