2.2.9 Sample Size Justification

The sample size for the topical DS107 Phase IIb study was informed from the post-hoc analysis of the Phase IIa study. NRS and EASI will be the primary and co-primary efficacy endpoints. The positive efficacy data over 4 weeks showed no sign of a plateau and suggests further improvements may be observed at Week 8. Dunnett's procedure will be used to allow simultaneous comparisons of each DS dose concentration vs. vehicle control.

The sample size was estimated from the Phase IIa results at Week 4/exit; the mean improvement and corresponding standard deviation for vehicle subjects were used to perform the following calculations. As shown below, 100 patients per treatment arm (300 patients in total) will be required to detect mean advantages of 3.03 units for NRS (10-point scale) and 6.6 units for EASI favoring DS107 vs. vehicle. This assumes a two-sided test with 80% power conducted at the 5% overall significance level with a Dunnett's adjustment for multiple doses.

Table 1. Sample Size Calculation

Two group Satterthwaite t-test: No Difference (unequal variances) (equal n's)		
	NRS	EASI
Overall Dunnett's Type I Error	0.026	0.026
1 or 2 sided test?	2	2
Target DS107 Mean Reduction, μ_1	3.030	6.600
Expected Vehicle Mean Reduction, μ_2	1.810	4.000
Mean Difference Goal, $\mu_1 - \mu_2$	1.220	2.600
Phase 2a DS107 Standard Deviation, σ_1	2.490	4.450
Phase 2a Vehicle Standard Deviation, σ_2	3.040	7.110
Power (%)	80	80
n per group	100	100

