2.2.12 Efficacy Analyses

Summary statistics by visit will be provided for all efficacy endpoints. For continuous efficacy endpoints, summary statistics will also be provided for change from baseline at each post-baseline visit. Results for the primary and secondary efficacy endpoints will be presented separately for mild and moderate AD as well as combined across mild and moderate AD strata. Models will include a baseline covariate for mild/moderate for all primary and secondary efficacy analyses. Models will be performed for the primary efficacy endpoint for the separate AD strata but not for the secondary efficacy endpoints.

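### Mild and moderate AD are tested in separate models and nothing estimates whether the effect differs by severity; at the planned effect, identical strata would split on significance in about half of trials per dose and endpoint

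*SAP*

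**What the plan says.** SAP 2.2.4.4 defines two subgroups by baseline IGA (2 is mild, 3 is moderate) and states: "Statistical testing for this subgroup analyses will be limited to the primary efficacy endpoint". SAP 2.2.12 confirms how this is done: "Models will be performed for the primary efficacy endpoint for the separate AD strata but not for the secondary efficacy endpoints". That section also puts mild/moderate into the overall models as a baseline covariate. In the code in SAP 2.2.12.1 severity (AD) appears as a main effect beside treatment and baseline NRS, with no treatment-by-severity term. EASI is to be analysed in the same way.

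For the level of testing, SAP 2.2.8 says that "all pairwise DS107 comparisons vs vehicle will be performed at the 0.026 level". SAP 2.2.12.4 covers multiplicity across doses, the two primary endpoints and the secondary and exploratory hierarchy, but does not mention the stratum tests.

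The only interaction named in either document's analysis text is treatment-by-visit (Protocol synopsis, 12.9.1 and 12.9.2). SAP 2.2.9 sizes the trial for the overall comparison; it gives neither power within a stratum nor an expected severity mix. Randomisation is stratified by site only (SAP 2.2.11.1).

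**The concern.** Fitting mild and moderate disease separately and testing each implies a question: is the effect the same in both? Two separate p-values do not answer it. A significant result in one stratum beside a non-significant one in the other is weak evidence of a difference, particularly when each stratum holds only part of the 100 patients per arm. The direct answer is an estimate of the difference between the two stratum effects with its interval, and the plan has none.

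At stake is how the Phase IIb result is read. If the strata disagree on significance, the planned outputs give no way to tell a real difference from the ordinary result of splitting an 80%-power trial in two.

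**Working it through.** **Inputs (SAP 2.2.9, 2.2.8).** Mean difference 1.22 (NRS) and 2.60 (EASI); SD for DS107 2.49 and 4.45; SD for vehicle 3.04 and 7.11; 100 per arm; two-sided 0.026 per dose. The severity split is not in the documents, so 50:50 is assumed and a range is shown.

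**Step 1: reproduce the plan's figure.** Unequal-variance t-test with Satterthwaite degrees of freedom, SE = √[(σ₁² + σ₂²)/n].
- NRS, n = 100: SE = √(15.4417/100) = 0.393; 1.22/0.393 = 3.10; power 80.5%.
- EASI, n = 100: SE = √(70.3546/100) = 0.839; 2.60/0.839 = 3.10; power 80.2%.

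Both match the stated 80%.

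**Step 2: power within a stratum at 50:50 (50 per arm).**
- NRS: SE = √(15.4417/50) = 0.556; 1.22/0.556 = 2.20, against a critical t of about 2.26; power 47.6%.
- EASI: SE = √(70.3546/50) = 1.186; 2.60/1.186 = 2.19, against about 2.27; power 47.3%.

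**Step 3: chance that exactly one stratum is significant.** The strata contain different patients, so this is p₁(1−p₂) + p₂(1−p₁). For NRS at 50:50: 2 × 0.476 × 0.524 = 0.499.

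| Split | NRS power in the two strata | Exactly one significant |
|---|---|---|
| 50:50 | 47.6%, 47.6% | 49.9% |
| 40:60 | 38.4%, 56.1% | 51.4% |
| 30:70 | 28.7%, 63.6% | 55.8% |
| 20:80 | 18.8%, 70.1% | 62.5% |

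EASI agrees within 0.2 percentage points.

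**Step 4: sensitivity (NRS, 50:50).**
- True effect, as a multiple of plan: 22% at 0.5, 40% at 0.75, 50% at 1, 43% at 1.25, 26% at 1.5.
- If baseline adjustment reduces the SD (assumed baseline-outcome correlation 0.3 to 0.6): 50% down to 43%.
- If 0.052, the alpha printed in the code, were the test level: 48%.
- Among simulated trials whose overall NRS comparison is significant: about 58%.

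**Step 5: false positives when there is no effect.** The count is 2 strata × 2 doses = 4 tests for NRS only, or 8 with EASI. If the tests were independent, 1 − 0.974⁴ = 10.0% and 1 − 0.974⁸ = 19.0%. They are not independent, because both doses are compared with the same vehicle patients. The correlation between the two dose statistics is σ₂²/(σ₁² + σ₂²) = 9.2416/15.4417 = 0.60 for NRS and 50.5521/70.3546 = 0.72 for EASI. Simulation with that correlation gives about 9% for four tests. For eight tests it gives 17% with NRS and EASI uncorrelated and 15% with an assumed correlation of 0.7.

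**Step 6: what an interaction test could do (NRS, 50:50).** SE = √[15.4417 × (1/50 + 1/50)] = 0.786. At two-sided 0.05, power for a between-stratum difference of 1.22 is Φ(1.22/0.786 − 1.96) = Φ(−0.41) = 34%. The difference detectable with 80% power is (1.96 + 0.8416) × 0.786 = 2.20, or 1.8 times the planned effect. When the effects are identical it would flag a difference in 5% of trials.

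**The case against.** Several objections have force.

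- **The one-half figure is conditional.** A reader might infer that about half of all trials with equal strata would mislead. That holds only near the planned effect, for one dose and one endpoint, and under an assumed split (Step 4). At the planned effect, however, 50:50 is the most favourable split.
- **Effectiveness needs both endpoints.** SAP 2.2.12.1 requires NRS and EASI together, so significance on one endpoint is not the SAP's definition of a working drug. Applying the joint rule within strata at 50:50 gives discordance of about 35% if the two test statistics are independent (2 × 0.225 × 0.775, where 0.225 = 0.476 × 0.473), rising to about 45% at an assumed correlation of 0.7. That is lower but still large.
- **Eight unadjusted tests with a 19% error rate would be too strong.** The SAP speaks of the primary efficacy endpoint in the singular, which may mean NRS only. Each test already sits at the Dunnett level for two doses, and the shared vehicle arm lowers the total. What is missing is adjustment across strata.
- **Population selection is not in the plan.** A reader might infer that the trial will choose between mild and moderate disease. No passage says so; success rests on the overall comparisons, and no rule compares stratum p-values.
- **There are partial safeguards.** Severity is a single pre-specified factor, secondary endpoints are not tested by stratum, combined results are shown alongside, and the model is said to provide intervals.

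None of this supplies an estimate of the difference between strata, so the core point stands.

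**Conclusion.** The point holds as a cheap improvement to the SAP. It is not a threat to the primary analysis. As written, the plan tests each severity stratum and cannot show whether the effect differs between them. The discordance figure rests on a true effect equal to plan and identical in both strata, the Phase IIa SDs and an assumed severity split. The false-positive range depends on whether EASI is included in the stratum testing, which the SAP should settle. The documents do not support reading the figure as a general property of the design, or as evidence that a wrong population would be taken forward.

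**What to change.** In SAP 2.2.4.4 and 2.2.12:

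1. Keep the primary model unchanged. The interaction belongs in a separate supportive model, because in the primary model default least-squares means would weight the two strata equally and could change the primary estimate.
2. Add a supportive FAS model for NRS and for EASI with a treatment-by-severity term. If the model is longitudinal, add the matching visit terms; the MODEL statement printed in SAP 2.2.12.1 has no visit term.
3. Report the Week 8 interaction estimate with its confidence interval for each dose, and show stratum effects with intervals from that same model.
4. Label any stratum p-values as descriptive and not to be compared between strata, and say whether they cover NRS only or NRS and EASI.

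The cost is a few lines of text and one extra model per endpoint. The SAP should state two limits. The interaction test has low power (Step 6), so a non-significant result does not show homogeneity. An interaction on absolute EASI change may also partly reflect the entry rule, since only moderate patients must have EASI of at least 12 (Protocol 7.2).

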2.2.5 Study Assessment Time Points

The study consists of seven protocol-specified visits which will be assessed as nominal visits from an analysis perspective:

- Visit 1/Screening visit (Day -30 to -1): Once informed consent has been obtained, the Investigator will assign a Patient Number and the subject will undergo the screening procedures. Following completion of a successful screening visit, patients will begin the comparative treatment period (8 weeks).
- Visit 2/Baseline (Day 0): At the start of the comparative treatment period, after confirmation of continued eligibility, patients will be randomly assigned to one of the three treatment regimens. Study medication is dispensed at Visit 2. The first application of study medication will be carried out at the site once all baseline assessments have been completed. The patient will carry out their second application of study medication in the evening of Day 0.
- Visits 3, 4 and 5: Follow-up visits at Week 2 (Day 14 ± 2 days), Week 4 (Day 28 ± 2 days) and Week 6 (Day 42 ± 2 days) respectively.
- Visit 6 – End of Treatment (EOT): Week 8 (Day 56 ± 2 days) for subjects who complete 8 weeks of treatment; earlier for subjects who discontinue treatment prematurely.
- Visit 7/Week 10: End of Study visit (Day 70 ± 3 days) for all subjects.
- Unscheduled Visits: Unscheduled visits may occur when a patient needs to make a visit in between the scheduled visit dates due to an AE, difficulty complying with the study protocol requirements, or a significant change in their disease state. All procedures that are medically necessary should be followed.

2.2.6 Methods for Handling Missing Data

The effects of missing efficacy data will be incorporated through the appropriate covariance structure from the GLMM. This will apply to continuous as well as binary endpoints.

A sensitivity analysis will be performed for Week 8/Exit outcome under the missing at not random (MNAR) assumption for the primary efficacy analyses using the FAS. The primary statistical analysis assumes “Missing At Random (MAR)” when handling missing data. The treatment effect obtained under the MAR assumption is essentially that which could have been reached if all patients had fully adhered to treatment or, in other words, the effect a patient may expect if they take the medication as directed. This is sometimes known as the ‘de jure’ or ‘efficacy’ estimand. Because of the lack of perfect adherence in practice, the ‘de facto’ or effectiveness treatment effect will also be estimated. This estimand includes assumptions regarding the treatment effects that could be expected to occur when patients discontinue treatment. The jump to reference method described by Carpenter et al. (J Biopharm Stat, 2013; 23(6):1352-71) will be used to estimate the de facto estimand, using the vehicle arm as the reference. This is based on the assumption that patients who discontinue from study drug have no alternative oral treatment option suitable for longer-term use and so their responses are likely to revert to those of the vehicle group. The sensitivity analyses for missing data will be performed on the FAS only.

2.2.7 Safety Monitoring

No safety monitoring committees are planned for the study.

2.2.8 Statistical Hypotheses

The original null hypothesis (H_0) for each analysis is the equality of the means for the three treatment groups. A global test was to be performed across all three treatment groups. The test will still be performed

The revised primary focus will be the separate comparisons of the two DS107 concentrations vs. vehicle control using a Dunnett’s correction (two-sided 97.4% confidence intervals and two-sided $p=0.026$) to reach statistical significance. The null hypotheses are the pairwise comparisons of the equality of the two DS107 concentrations vs. vehicle. Dunnett’s procedure will be used to adjust for the multiple comparisons. The overall 5% Type I error rate is controlled for by the Dunnett’s correction for multiple comparisons.

Testing between the two active groups will be considered as descriptive statistics.

All statistical testing will be two-sided; global tests will be performed at the 0.05 level while all pairwise DS107 comparisons vs vehicle will be performed at the 0.026 level.

2.2.9 Sample Size Justification

The sample size for the topical DS107 Phase IIb study was informed from the post-hoc analysis of the Phase IIa study. NRS and EASI will be the primary and co-primary efficacy endpoints. The positive efficacy data over 4 weeks showed no sign of a plateau and suggests further improvements may be observed at Week 8. Dunnett's procedure will be used to allow simultaneous comparisons of each DS dose concentration vs. vehicle control.

The sample size was estimated from the Phase IIa results at Week 4/exit; the mean improvement and corresponding standard deviation for vehicle subjects were used to perform the following calculations. As shown below, 100 patients per treatment arm (300 patients in total) will be required to detect mean advantages of 3.03 units for NRS (10-point scale) and 6.6 units for EASI favoring DS107 vs. vehicle. This assumes a two-sided test with 80% power conducted at the 5% overall significance level with a Dunnett's adjustment for multiple doses.

Table 1. Sample Size Calculation

Two group Satterthwaite t-test: No Difference (unequal variances) (equal n's)		
	NRS	EASI
Overall Dunnett's Type I Error	0.026	0.026
1 or 2 sided test?	2	2
Target DS107 Mean Reduction, μ_1	3.030	6.600
Expected Vehicle Mean Reduction, μ_2	1.810	4.000
Mean Difference Goal, $\mu_1 - \mu_2$	1.220	2.600
Phase 2a DS107 Standard Deviation, σ_1	2.490	4.450
Phase 2a Vehicle Standard Deviation, σ_2	3.040	7.110
Power (%)	80	80
n per group	100	100

2.2.10 Interim Analyses

An interim analysis is planned to assess the primary and co-primary efficacy endpoint futility, to assess the original primary efficacy endpoint, and to adjust

sample size. The sample size may be increased at the interim analysis (conducted after n=150 complete Week 8/Exit) to update primary efficacy endpoint assumptions and to achieve at least 80% power and two-sided 2.6% Type I error (to allow for each DS107 dose to be separately compared to vehicle control).

2.2.11 Randomization/Unblinding

2.2.11.1 Randomization Methodology

Approximately 300 patients will be randomized to the three blinded treatment groups in a 1:1:1 ratio as follows:

- Treatment group A: 1% DS107 cream applied topically to all affected or commonly affected areas twice-daily for 8 weeks
- Treatment group B: 5% DS107 cream applied topically to all affected or commonly affected areas twice-daily for 8 weeks
- Treatment group C: Vehicle cream applied topically to all affected or commonly affected areas twice-daily for 8 weeks.

A randomization list, permuted blocks and stratified by site was generated by HMD Clinical ([name]). The randomization schedule with study drug assignments was generated prior to the start of the study and will be known only to the individuals responsible for labelling the study drug, the statisticians generating the schedule and the IWRS team responsible for implementing the schedule. The IWRS will assign a medication kit number to each patient and the contents will be based on the randomization code.

2.2.11.2 Unblinding

All study site personnel, as well as the personnel involved in the monitoring or conduct of the study, will be blinded to the individual patient treatment assignments. Randomisation details will be kept strictly confidential, accessible only in an emergency to authorized persons, until the time of formal unblinding. The blinded code for the trial will be broken only after all patient data has been recorded and verified and the database locked.

Emergency unblinding will be carried out through the IWRS system with relevant site personnel and pharmacovigilance monitors provided with the required system access to carry out unblinding.

Any unblinding (and reason for unblinding) prior to database lock will be reported in the final CSR.

2.2.12 Efficacy Analyses

Summary statistics by visit will be provided for all efficacy endpoints. For continuous efficacy endpoints, summary statistics will also be provided for change from baseline at each post-baseline visit. Results for the primary and secondary efficacy endpoints will be presented separately for mild and moderate AD as well as combined across mild and moderate AD strata. Models will include a baseline covariate for mild/moderate for all primary and secondary efficacy analyses. Models will be performed for the primary efficacy endpoint for the separate AD strata but not for the secondary efficacy endpoints.

- Change from baseline in Eczema Area and Severity Index (EASI) in treated population compared to vehicle population at Weeks 2, 4, 6 and 10 and subject's last treatment visit. These will be analyzed using the similar PROC MIXED code as described in the primary endpoint section. Three separate models will be done using the same PROC MIXED code for the change from baseline to Week 2, 4 and 6, for the change from baseline to Week 10, and for the change from baseline to last treatment visit.
- Proportion of patients achieving an IGA score of 0 (clear) or 1 (almost clear) and a decrease of at least 2 points in IGA in treated population compared to vehicle population from baseline to Week 2, 4, 6, 8 and 10 and change from baseline to subject's last treatment visit. These analyses will be performed using the same PROC GENMOD code described above. Three separate models will be done for the change from baseline to Week 2, 4, 6 and 8, for the change from baseline to Week 10, and for the change from baseline to last treatment visit.

- Proportion of patients achieving a decrease of at least 2 points in IGA in treated population compared to vehicle population from baseline to Week 2, 4, 6, 8, 10, and change from baseline to subject's last treatment visit. These analyses will be performed using the same PROC GENMOD code described above. Three separate models will be done using the same PROC GENMOD code for the change from baseline to Week 2, 4, 6 and 8, for the change from baseline to Week 10 and for the change from baseline to last treatment visit.
- Change from baseline IGA in treated population compared to vehicle population at Weeks 2, 4, 6, 8 and 10 and subject's last treatment visit. These will be analyzed using the same PROC MIXED using code similar to the following, with CFB_IGA and B_IGA representing the change from baseline and the baseline IGA, respectively. Method=ml is the maximum likelihood estimate.

```
proc mixed method =ml data= FAS;
class trt visit AD;
model CFB_IGA= trt AD B_IGA/CL alpha=0.052;
lsmeans trt*visit / diff CL;
run;
```

Three separate models will be done using the same PROC MIXED code for the change from baseline to Week 2, 4, 6 and 8, for the change from baseline to Week 10 and for the change from baseline to last treatment visit.

The method for controlling the Type I error rate is provided in Section 2.2.12.4.

